7.1.3.1 Laboratory Safety Evaluations (Hematology, Chemistry and Urinalysis)

Laboratory tests for hematology, chemistry and urinalysis are specified in [Table 4](#).

Table 4 Laboratory Tests

Hematology	Chemistry	Urinalysis	Other
Hematocrit	Albumin	Blood	Serum β -Human Chorionic Gonadotropin (β -hCG) (If applicable)
Hemoglobin	Alkaline phosphatase	Glucose	Urine β -Human Chorionic Gonadotropin (β -hCG) (If applicable)
Platelet count	Alanine aminotransferase (ALT)	Protein	Follicle Stimulating Hormone (FSH) (if applicable)
WBC (total and differential)	Aspartate aminotransferase (AST)	Specific gravity	Hepatitis
PT/aPTT (Part II screening only)	Bicarbonate	Microscopic exam, if abnormal results are noted	HIV
	Calcium		Urine/Blood Drug Screen (per site SOP)
	Chloride		
	Creatinine		
	Glucose		
	Phosphorus		
	Potassium		
	Sodium		
	Total Bilirubin		
	Direct Bilirubin, if total bilirubin is elevated above the upper limit of normal		
	Total protein		
	Urea/Blood Urea Nitrogen (BUN)		

In each Part, subjects will fast from all food and drink except water for at least 4 h prior to screening, pre-dose and post-trial laboratory safety evaluations.

7.1.3.2 Pharmacokinetic/Pharmacodynamic Evaluations

Quantification of tracer in plasma will be performed to obtain the input function for PET tracer kinetic modeling. In addition, the decision as to which Part III samples collected will be assayed for exploratory evaluations will be collaboratively determined by the appropriate departments within the Sponsor's organization.

7.1.3.2.1 Blood Collection for [¹¹C]MK-6884 Tracer Kinetics (Parts I and II)

Prior to dosing, IV catheter will be placed for Part I subjects and radial arterial catheters will be placed for Part II subjects for arterial blood sampling. The clinical site SOP will be followed for collection and analysis of blood samples. Samples will be collected and analyzed on site.

7.1.3.2.2 Blood Collection for Plasma Donepezil or Rivastigmine (Part III)

Blood sample for determination of plasma donepezil or rivastigmine levels should be taken no more than 90 minutes prior to [¹¹C]MK-6884 administration. Sample collection, storage and shipment instructions for plasma samples will be provided in the Operations Manual.

7.1.3.2.3 Blood Collection for Plasma AChE Activity (Part III)

Blood samples for determination of erythrocyte acetylcholinesterase (RBC-AChE) activity should be taken no more than 90 minutes prior to [¹¹C]MK-6884 administration. Sample collection, storage and shipment instructions for plasma samples will be provided in the Operations Manual.

7.1.3.3 Planned Genetic Analysis Sample Collection

Sample collection, storage and shipment instructions for Planned Genetic Analysis samples will be provided in the appendix Section 12.2

7.1.3.4 Future Biomedical Research Sample Collection

The following specimens are to be obtained as part of Future Biomedical Research:

Leftover DNA for future research.

7.1.4 Other Procedures

7.1.4.1 Withdrawal/Discontinuation

The investigator or trial coordinator must notify the Sponsor when a subject has been discontinued/withdrawn from the trial. If a subject discontinues for any reason at any time during the course of the trial, the subject may be asked to return to the clinic (or be contacted) for a post-trial visit (approximately 14 days after the last dose of trial drug is given) to have the applicable procedures conducted. However, the investigator may decide to perform the post-trial procedures at the time of discontinuation or as soon as possible after discontinuation. If the post-trial visit occurs prior to 14 days after the last dose of trial drug is given, the investigator should perform a follow-up phone call 14 days after the last dose of trial drug to determine if any adverse events have occurred since the post-trial clinic visit. Any adverse events which are present at the time of discontinuation/withdrawal should be followed in accordance with the safety requirements outlined in Section 7.2 - Assessing and Recording Adverse Events.

7.1.4.1.1 Withdrawal From Future Biomedical Research

Subjects may withdraw their consent for Future Biomedical Research and have their specimens and all derivatives destroyed. Subjects may withdraw consent at any time by contacting the principal investigator for the main trial. If medical records for the main trial are still available, the investigator will contact the Sponsor using the designated mailbox ([contact]), and a form will be provided by the Sponsor to obtain appropriate information to complete specimen withdrawal. Subsequently, the subject's specimens will be removed from the biorepository and be destroyed. A letter will be sent from the Sponsor to the investigator confirming the destruction. It is the responsibility of the investigator to inform the subject of completion of destruction. Any analyses in progress at the time of request for destruction or already performed prior to the request being received by the Sponsor will continue to be used as part of the overall research trial data and results. No new analyses would be generated after the request is received.

In the event that the medical records for the main trial are no longer available (e.g., if the investigator is no longer required by regulatory authorities to retain the main trial records) or the specimens have been completely anonymized, there will no longer be a link between the subject's personal information and their specimens. In this situation, the request for specimen destruction cannot be processed.

7.1.4.2 Blinding/Unblinding

This is an open label trial; there is no blinding for this trial.

7.1.4.3 Domiciling

Parts I and III: Subjects will report to the research center on Day -1 (Part I) or on Day 1 (Part III) and will be discharged after completion of all post-dose study procedures following the scanning session on Day 1. At the discretion of the investigator, subjects may be

requested to stay longer or return to the unit in the event of a technical failure that prevents tracer administration or scanning.

Part II: Subjects will report to the research center on Day -1 and will be discharged after completion of all post-dose study procedures following Scan 1 and Scan 2. At the discretion of the investigator, subjects may be requested to stay longer or return to the unit in the event of a technical failure that prevents tracer administration or scanning.

7.1.4.4 Calibration of Critical Equipment

The investigator or qualified designee has the responsibility to ensure that any critical device or instrument used for a clinical evaluation/test during a clinical trial that provides important information about inclusion/exclusion criteria and/or safety or efficacy parameters shall be suitably calibrated and maintained to ensure that the data obtained is reliable and/or reproducible. Documentation of equipment calibration must be retained as source documentation at the trial site.

Critical Equipment for this trial includes:

MRI/PET/CT Scanners and related imaging equipment, equipment for measuring blood pressure, ECG machine, HPLC system, Gamma Counter, Centrifuge.

7.1.5 Visit Requirements

Visit requirements are outlined in Section 6.0 - Trial Flow Chart. Specific procedure-related details are provided above in Section 7.1 - Trial Procedures.

7.1.5.1 Screening (Part I, Part II and Part III)

Within approximately 4 weeks prior to randomization, potential subjects will be evaluated to determine that they fulfill the entry requirements as set forth in Section 5.1.

Screening procedures may be repeated after consultation with the Sponsor. In Parts II and III, a baseline MRI scan of the brain will be obtained for region-of-interest (ROI) delineation and to make sure the MRI scan is consistent with a diagnosis of AD (Part III only).

7.1.5.2 Treatment Period (Part I, Part II, and Part III)

In Parts I, II, and III, dosing and study procedures may be conducted any time during the day as the PET scan outcome measures are relatively resistant to the impact of diurnal variations in physiology.

Part I

Pre-dose

An IV catheter will be placed for injection of the radiotracer and venous blood sampling.

Dosing/Scanning

A single, open-label dose of $\leq 4.9 \mu\text{g}$ [^{11}C]MK-6884 with a radiation dose $\sim 370 \text{ MBq}$ will be administered by IV injection through an indwelling venous catheter while the subject is lying supine on the imaging table. Immediately following the [^{11}C]MK-6884 administration, a series of whole body PET images will be obtained over a period of up to approximately 120 minutes. CT scans will be obtained at each bed position, for attenuation correction.

The sequence of procedures that should be followed in Part I (refer to Study Flowchart in Section 6.0) is outlined in [Table 5](#).

Table 5 Part I Procedures

Time Period	Description
-90 to -10 minutes	
-All procedures requiring needle sticks will be completed, including antecubital venous lines.-Subjects should be asked to micturate immediately prior to the next time period.
Approximately 30 minutes pre-dose	
-Subjects will rest supine on the imaging table while baseline vital signs and ECGs are obtained per the study flowchart (Section 6.0).-Venous blood sample will be drawn before tracer administration for baseline laboratory safety evaluations (up to 24 hours prior).-A whole body CT scan is obtained (the time of the CT scan can be at the discretion of the investigator, target within 5 min before acquisition)
Time “0”	[^{11}C]MK-6884 administration, PET scan initiated
0 to ~ 120 minutes	
Subjects will be asked to remain motionless on the imaging table while the scans are acquired.-HR, BP, and 12-lead ECGs will be obtained during this time period per the study flowchart (Section 6.0)-Venous blood samples will be collected for measurement of radioactivity associated with the parent tracer and its metabolites (Section 6.0)
End of scanning sessions	HR, BP, EGG and blood for laboratory safety evaluations will be collected per the study flowchart (Section 6.0). Indwelling venous catheter will be removed.

All images will be acquired using the HI-Rez Biography PET/CT scanner. First, a CT scout will be acquired to set the axial field of view (FOV). The axial FOV should extend from the top of the head to the middle of the thighs (~ 8 bed positions). Then, a low current CT will be acquired for both PET attenuation correction and anatomical information. Following the CT 3D PET images will be acquired sequentially for an overall study duration of approximately 2 hours.

WB 1-3: 30s/bed (~4 min per WB)
WB 4-6: 60s/bed (~8 min per WB)
WB 7-8: 120s/bed (~16 min per WB)
WB 9: 240s/bed (~32 min per WB)

After this sequence of PET acquisitions, the subject will be moved out of the camera and will be encouraged to void their urine. The actual times of scanning and the acquisition sequence may be varied by the investigator, as indicated by the data that emerges during the course of the study – See Section 7.1.5.5. In order to use the whole body PET images for dosimetry calculations, the dose calibrator and PET scanner will be cross-calibrated.

Catheters will be removed after all of the procedures requiring venous access have been completed.

Postdose

Subjects may stay overnight at the discretion of the investigator.

Part II

Pre-dose

Prior to administration of [¹¹C]MK-6884, a trained staff member will place an arterial catheter in a radial artery for the collection of blood samples. A topical anesthetic may be used to reduce some of the discomfort associated with insertion of the catheter. The staff member placing the line may also inject a small amount of lidocaine subcutaneously to further reduce any discomfort when the actual catheter is placed. The IV catheter for tracer injection will be placed contralateral to the radial arterial catheter and the IV catheter for arterial blood sampling.

Dosing/Scanning

A low-dose CT scan of the brain will be performed to enable attenuation correction of the emission scan. Separate single, open-label doses of [¹¹C]MK-6884 will be administered by IV injection through an indwelling venous catheter while the subject is lying supine on the imaging table (dose may be adapted based on the data from Part I). The brain PET scan will be initiated along with the initiation of the tracer injection. The sequence of procedures that should be followed in Part II (refer to Study Flowchart in Section 6.0) is outlined in [Table 6](#).

Table 6 Part II Procedures

Time Period	Description
-90 to -10 minutes	
 -All procedures requiring needle sticks will be completed, including antecubital venous and arterial lines. -Subjects should be asked to micturate immediately prior to the next time period.
Approximately 30 minutes pre-dose	
 -Subjects will rest supine on the imaging table while baseline vital signs and ECGs are obtained per the study flowchart (Section 6.0). -Venous blood samples will be drawn before tracer administration for baseline laboratory safety evaluations (up to 24 hours prior). This is done prior to the first dose only if both doses are done on the same day or if both doses are done on consecutive days. If the second dose is done on a different non-consecutive day, blood samples should be obtained for baseline laboratory safety evaluations prior to the second scan as well. -A brain attenuation CT scan is obtained (the time of the CT scan can be at the discretion of the investigator)
Time “0”	[¹¹ C]MK-6884 administration ¹ , PET scan initiated
0 - ~90 min	
 -Subjects will be asked to remain motionless on the imaging table while the scans are acquired. -HR, BP, and 12-lead ECGs will be obtained during this time period per the study flowchart (Section 6.0) -Arterial blood samples will be collected for tracer metabolism counts per the study flowchart (Section 6.0) - Arterial blood samples will be collected for radioactivity counts per the study flow chart (Section 6.0).
End of scanning session	
 - HR, BP, and ECG will be collected per the study flow chart (Section 6.0). Indwelling catheter will be removed. -Venous blood samples will be drawn for laboratory safety evaluations. This is done at the end of the second scan only if both doses/scans are done on the same day or if both doses/scans are done on consecutive days. If the second scan is done on a different non-consecutive day, blood samples should be obtained at the end of the first scan as well for laboratory safety evaluations.

¹ Sequence procedures for the second dose (to be administered at least 3 hours after the first dose) will follow the time frame as for the first dose. If second dose/scanning session occurs on a different day due to difficulties performing both scans in one day, then all procedures starting from row 1 of this table will be followed.

A brain PET scan will be initiated immediately following each dosing. For each scanning session, subjects will be positioned on the scanner bed with the head within the center of axial and transaxial fields of view. The head will be restrained to reduce movement artifacts during the scan. Baseline sensory conditions (dimmed room lighting, reduced noise) will be imposed and maintained throughout the session.

Catheters will be removed after all of the procedures requiring arterial and venous access have been completed.

Postdose

Subjects may stay overnight after the day of scanning at the discretion of the investigator.

Part III

Pre-dose

An IV catheter will be placed for injection of the radiotracer.

Dosing/Scanning

In Part III, a single IV dose of approximately 370 MBq (10 mCi, $\leq 4.9 \mu\text{g}$) [^{11}C]MK-6884 will be administered. A single brain scan will be performed after the dose, and positron emission images of the brain will be obtained for approximately 90 minutes after the administration of [^{11}C]MK-6884 to verify the BP_{ND} of the [^{11}C]MK-6884 ligand.

The sequence of procedures that should be followed in Part III (refer to Study Flowchart in Section 6.0) is outlined in [Table 7](#).

Table 7 Part III Procedures.

Time	Description
Approximately 2 hours to 90 minutes pre-dose	-Venous blood sample will be drawn before tracer administration for baseline laboratory safety evaluations.
-90 to -10 minutes	-Note all procedures requiring needle sticks (including antecubital venous lines) will be completed -Venous bloods sample will be drawn for evaluation of plasma donepezil/rivastigmine level and RBC-AChE activity during this period. -Subjects should be asked to micturate immediately prior to the next time period.
Approximately 30 minutes pre-dose	-Subjects will rest supine on the imaging table while baseline vital signs and ECGs are obtained per the study flowchart (Section 6.0). -A brain attenuation CT scan is obtained (the time of the CT scan can be at the discretion of the investigator) ¹
Time “0”	[^{11}C]MK-6884 administration, PET/CT scan initiated

Time	Description
0 to ~ 90 minutes	Subjects will be asked to remain motionless on the imaging table while the scans are acquired. ¹ -HR, BP, and 12-lead ECGs will be obtained during this time period per the study flowchart (Section 6.0)
End of scanning sessions	HR, BP, ECG and blood for laboratory safety evaluations will be collected per the study flowchart (Section 6.0). Indwelling venous catheter will be removed.

¹ Every effort should be made to get a full dynamic scan for 90 minutes (if required based on available data from the ongoing trial). If an AD subject cannot tolerate the full duration of 90 minutes, as determined by the investigator, or, an unexpected intolerance event occurs at or after 60 minutes into a full scan, the scan can be concluded at or after 60 minutes. PET data for such a shortened scan should be reconstructed following the same protocol as a normal scan, without inclusion of the truncated time frames.

A brain PET scan will be initiated immediately following dosing. For the scanning session, subjects will be positioned on the scanner bed with the head within the center of axial and transaxial fields of view. The head will be restrained to reduce movement artifacts during the scan. Baseline sensory conditions (dimmed room lighting, reduced noise) will be imposed and maintained throughout the session.

Catheters will be removed after all of the procedures requiring venous access have been completed.

Postdose

Subjects may stay overnight at the discretion of the investigator.

7.1.5.3 Post-Trial

Post-study procedures will be performed either shortly after the last scanning session, or just prior to discharge which may be at ~ 24 hours post final dose (if the subject is kept overnight at the investigator's discretion) (see the Study Flowchart in Section 6.0). Assessment for potential adverse experiences will be conducted at ~24 hours post dose either by phone or at the clinic, followed by an additional phone call conducted at 14 days post final dose.

7.1.5.4 Critical Procedures Based on Trial Objectives: Timing of Procedure

For this trial, the blood sample collections for [¹¹C]MK-6884/tracer kinetics (in Parts I and II) and the PET scans (in Parts I, II, and III) are the critical procedures.

At any postdose time point, the blood sampling for tracer kinetics and PET scans need to be performed as close to the exact time point as possible. When multiple procedures are scheduled for the same time, the collection of venous (Part I) or arterial (Part II) blood samples will have the highest priority. All other procedures should be completed as close to the prescribed/scheduled time as possible. Trial procedures can be performed prior or after the prescribed/scheduled time.

The order of priority can be changed during the trial with joint agreement of the investigator and the Sponsor Clinical Director.

Any nonscheduled procedures required for urgent evaluation of safety concerns take precedence over all routine scheduled procedures.

7.1.5.5 Trial Design/Dosing/Procedures Modifications Permitted within Protocol Parameters

This is a Phase I assessment of MK-6884 in humans, and the pharmacokinetic, pharmacodynamic and safety profiles of the compound is still being elucidated. This protocol is written with some flexibility to accommodate the inherent dynamic nature of Phase I clinical trials. Modifications to the dose, dosing regimen and/or clinical or laboratory procedures currently outlined below may be required to achieve the scientific goals of the trial objectives and/or to ensure appropriate safety monitoring of the trial subjects.

As such, some alterations from the currently outlined radiation dose and/or dosing regimen may be permitted based on newly available data, but the tracer mass dose as well as yearly effective dose may not exceed those limits currently outlined in the protocol. Specifically, any upward titration in the radiation dose for Parts II and III may occur if needed based on Part I data as long as it remains below the yearly acceptable limits of radiation exposure.

- Repeat of or adjustment in the dose of the trial drug administered in any given period/panel
- Omission of one part of the study or a dose within Part II
- Adjustment of the dosing interval (Part II)
- Instructions to take trial drug with or without food or drink may also be modified based on newly available data
- Changes to the time interval between dosing and PET scans
- Changes to the scanning protocol
- Changes to tracer kinetics sampling timepoints

If it is determined that incomplete or aberrant data has been captured during the PET measurements at any post-randomization trial visit, the subject may be asked to repeat the treatment/scan. The evaluation to determine whether the treatment/scan is to be repeated will be done on an individual basis per subject, and the decision will be reached by mutual agreement of the Sponsor and investigator. Up to two (2) treatment/scan per subject may be repeated. Repeating treatment/scan may result in an increase of the subject's cumulative exposure and/or may increase the total blood volume with approximately 50 mL per repeat in Part I, approximately 90 mL in Part II, and approximately 33 mL in Part III. The resulting exposure or blood volume increases will be deemed acceptable by the Sponsor and investigator for that subject. The total blood volume collected should remain <500 mL. A subject may be discontinued from the trial and be replaced at the investigator's discretion after one failed repeat treatment/scan.

The blood sampling scheme for tracer kinetics currently outlined in the protocol may be modified during the trial based on newly available data (e.g., to obtain data closer to the time of peak plasma concentrations). If indicated, these collected samples may also be assayed in an exploratory manner for metabolites and/or additional pharmacodynamic markers.

Up to additional 50 mL of blood may be drawn for safety, pharmacokinetic, and/or pharmacodynamic analyses. The total blood volume withdrawn from any single subject will not exceed the maximum allowable volume during his/her participation in the entire trial (Section 12.4).

The timing of procedures for assessment of safety procedures (e.g., vital signs, ECG, safety laboratory tests, etc.) currently outlined in the protocol may be modified during the trial based on newly available safety, tolerability, pharmacokinetic or pharmacodynamic data (e.g., to obtain data closer to the time of peak plasma concentrations). Additional laboratory safety tests may be added to blood samples previously drawn to obtain additional safety information (e.g., adding creatinine kinase to serum chemistry panel that was already drawn). These changes will not increase the number of trial procedures for a given subject during his/her participation in the entire trial.

It is understood that the current trial may employ some or none of the alterations described above. Any alteration made to this protocol to meet the trial objectives must be detailed by the Sponsor in a letter to the Trial File and forwarded to the investigator for retention. The letter may be forwarded to the IRB/ERC at the discretion of the investigator.

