5.9 Subject Replacement Strategy

If a subject discontinues from the trial, a replacement subject may be enrolled if deemed appropriate by the investigator and Sponsor. The replacement subject will generally receive the same treatment or treatment sequence (as appropriate) as the subject being replaced. The replacement subject will be assigned a unique treatment/randomization number. The trial site should contact the Sponsor for the replacement subject's treatment/randomization number.

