8.2 Statistical Analysis Plan

The statistical analysis of the data obtained from this study will be conducted by, or under the direct auspices of, the Early Clinical Development Statistics Department in collaboration with the Pharmacology Imaging and Translational Medicine Departments of the Sponsor.

The analysis of the data obtained in Part I of this study will be the responsibility of the Leuven PET center. The analysis of the data obtained in Part II and Part III of the study will be the responsibility of the Merck Translational Imaging Biomarkers Department.

If, after the study has begun, changes are made to the statistical and image analysis plan stated below, then these deviations to the plan will be listed, along with an explanation as to why they occurred, in the Clinical Study Report (CSR).

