8.2.3 Approaches to Analyses

The following populations are defined for the analysis and reporting of data. All subjects will be reported, and their data analyzed, according to the treatment(s) they actually received.

All Subjects as Treated (AST) - All subjects who received at least one dose of the investigational drug. This population will be used for assessments of safety and tolerability.

Per-Protocol (PP) – The set of data generated by the subset of subjects who comply with the protocol sufficiently to ensure that these data will be likely to exhibit the effects of treatment, according to the underlying scientific model. Compliance covers such considerations as exposure to treatment, availability of measurements and absence of major protocol deviations. Major protocol deviations will be identified to the extent by individuals responsible for data collection/compliance, and its analysis and interpretation. Any subjects or data values excluded from analysis will be identified, along with their reason for exclusion, in the CSR. At the end of the study, all subjects who are compliant with the study procedure as aforementioned and have available data from at least one treatment will be included in the primary analysis dataset. This population will be used for assessments of pharmacodynamics.

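### The repeat-and-replace rule for 'aberrant' PET data is not blinded to the Part II result and does not say which scan counts, so selection on test-retest difference is possible

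*Combined protocol and SAP*

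**What the plan says.** Section 7.1.5.5 gives two triggers for a repeat: "If it is determined that incomplete or aberrant data has been captured during the PET measurements at any post-randomization trial visit, the subject may be", after which the sentence permits a second attempt at the treatment or scan. Each case is considered individually, and "the decision will be reached by mutual agreement of the Sponsor and investigator". The allowance is generous: "Up to two (2) treatment/scan per subject may be repeated". Replacement follows: "A subject may be discontinued from the trial and be replaced at the investigator's discretion after one failed repeat treatment/scan". Section 5.9 has a general rule: "If a subject discontinues from the trial, a replacement subject may be enrolled if deemed appropriate by the investigator and Sponsor".

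Four other parts of the plan bear on this.

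- **Endpoint.** Section 8.2.4 defines T-RT variability as twice the absolute difference between the two scans divided by their sum, in percent. Section 8.2.1 compares the average with 20%.
- **Who sees the data.** Under Section 8.2, "The analysis of the data obtained in Part II and Part III of the study will be the responsibility of the Merck Translational Imaging Biomarkers" group, which belongs to the sponsor. Section 2.1 starts image analysis once 3 healthy subjects in Part II are complete, while the Part is still running.
- **Analysis set.** Section 8.2.3 uses a per-protocol set for pharmacodynamics. Excluded subjects and values, with reasons, go in the clinical study report (CSR).
- **Other records.** Section 8.2 requires departures from the analysis plan to be listed and explained in the CSR. Section 7.1.5.5 requires a letter to the Trial File for alterations to the protocol.

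**The concern.** *Incomplete* is a separate trigger, so *aberrant* must cover scans that ran to completion but look wrong. In Part II the quantity being estimated is the disagreement between two scans. If *aberrant* is judged after the index has been calculated, a large disagreement is an obvious reason to suspect a scan, and the decision then depends on the outcome. The sponsor shares the repeat decision and its imaging group calculates the index. Nothing keeps those two tasks apart, and nothing fixes which scan is used after a repeat.

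A re-draw prompted by a large difference pulls down the expected mean T-RT, although an individual re-draw can come out worse. The 20% limit is the only numeric success criterion in the hypotheses. The tracer is meant to support receptor occupancy measurement (Section 4.1.1), so understated variability would carry into the planning of later studies.

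**Working it through.** The plan has no sample-size or power figure to reproduce (Section 8.2.6), so the check simulates its own T-RT formula and its own limit.

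**From the documents:** at least 6 subjects and at most 10 in Part II; T-RT per subject = 2|test − retest| / (test + retest) × 100; success if the mean is 20% or less; up to two repeats per subject; replacement possible after one failed repeat.

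**Assumed, because the documents are silent:** lognormal index values with independent errors; the within-subject CV; the T-RT value at which a pair is flagged; the share of flagged pairs acted on.

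**Step 1, error size.** For two normal errors with SD s, the mean absolute difference is 2s/√π = 1.128s. A mean T-RT of 25% therefore needs a CV of about 25/1.128 = 22.2%. On the log scale this is √ln(1 + 0.222²) ≈ 0.219. The formula compresses large differences slightly, so the simulated true mean is about 24.3%.

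**Step 2, how often a pair exceeds 40%.** The formula equals 2·tanh(D/2), where D is the absolute log difference. It exceeds 0.40 when D > 2·atanh(0.20) = 0.405. The SD of the log difference is 0.219 × √2 = 0.310, so z = 0.405/0.310 = 1.31 and the two-sided probability is about 0.19. That is 6 × 0.19 ≈ 1.1 flagged pairs per trial. The chance of at least one is 1 − 0.81⁶ ≈ 72%.

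**Step 3, simulation with 6 pairs.** A flagged retest is re-drawn once. In the replacement rows, a pair still above the trigger is replaced by a new subject's pair.

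| Rule (40% trigger) | P(mean ≤ 20%) | Expected mean |
|---|---|---|
| No repeats | about 29% | 24.3% |
| All flagged retests repeated once | about 52% | 20.1% |
| As above, then replacement | about 66% | 18.2% |
| A quarter of flagged pairs acted on | about 34% | 23.3% |
| As above, then replacement | about 37% | 22.8% |

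**Step 4, other assumptions.**

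- With every flagged pair acted on, a 30% trigger gives about 62% (85% with replacement), a 50% trigger about 41% (46%) and a 60% trigger about 35% (36%).
- With the true mean set to exactly 25.0% and replacements limited by the maximum of 10 subjects, the 40% trigger gives 27% without repeats, 50% with one repeat and 68% with replacement.
- With a true mean of about 15%, the 40% trigger moves the pass probability only from about 87% to 91%, because a pair exceeds 40% about 3% of the time.

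The expected mean fell in every scenario. The amount depends on the trigger and on how often it is used.

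**The case against.** A reader might infer that the protocol plans to remove discordant pairs. It does not say so. The clause speaks of data captured during PET measurement and of a failed repeat scan. It applies to all three Parts, and two of them have no test-retest pair. An acquisition-fault reading is natural. Discordance as the trigger is an inference about what the words allow.

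The stated response to unexpected variability is to add up to 4 subjects (Sections 2.1 and 4.2.1), not to discard any.

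A reader might also infer that the per-protocol definition permits dropping discordant pairs, since it keeps only those that "comply with the protocol sufficiently to ensure that these data will be likely to exhibit the effects of treatment, according to the underlying scientific model". That over-reads Section 8.2.3. Membership turns on exposure, available measurements and absence of major deviations, and a large T-RT difference is none of these. The same section puts compliant subjects with data from at least one treatment into the primary dataset, which on its face retains a scanned subject who is later replaced.

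Practical limits apply too: no more than two arterial lines per subject (Section 7.1.2) and at most 10 subjects in Part II (Table 3). With 6 subjects and a point criterion, a tracer with a true mean near 25% already passes more than a quarter of the time without any repeat.

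These arguments reduce the likelihood and the severity. They do not close the route. None defines *aberrant* or *failed*, separates the judgement from the index, or says which of three or four scans forms the pair. The reporting duties act after the event, and a scan superseded by a repeat might not be listed as an exclusion at all.

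**Conclusion.** The concern holds as an open route to outcome-dependent selection in the Part II T-RT result. The documents do not support the stronger claim that discordant pairs will be swapped out or that the result will be biased. The direction is clear: acting on large differences lowers the expected mean that is compared with 20%. The size rests wholly on assumptions. With a true mean near 25% and a 40% trigger, the pass probability rises from about 29% to 52% (66% with replacement) if the rule is used every time, and to 34% (37%) if it is used a quarter of the time. It changes little when the tracer is comfortably repeatable. This should be fixed, but in a small estimation study with disclosure already required it does not undermine the design.

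The difference between Sections 5.9 and 7.1.5.5 on replacement is minor. One refers to the investigator and sponsor together, the other to the investigator's discretion. Section 5.9 also has the site obtain the replacement's number from the sponsor, so the sponsor is involved either way.

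**What to change.** - **Section 7.1.5.5.** Define *aberrant* and *failed* as documented technical failures, for example batch or quality-control failure, injection fault, motion, scanner fault, blood-line failure or a truncated scan. Require the judgement to be recorded before, or without sight of, any V_T, BP_ND, SUVR or T-RT value for that subject.
- **Sections 8.2.3 and 8.2.4.** Compute the primary T-RT from the first two technically adequate scans of every Part II subject, including any subject later replaced.
- **Reporting.** State the number of repeats and replacements and the reason for each. Add one sensitivity T-RT based on first-acquired pairs where both scans can be quantified. A table with repeats substituted would add little, because permitted repeats are already in the primary result.
- **Sections 5.9 and 7.1.5.5.** Reconcile the wording on who decides replacement.

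The cost is protocol and SAP wording plus one short table, with no extra subjects, scans or radiation. The downside is that an anomalous scan with no documented technical cause stays in the primary T-RT, so the reported figure may be slightly less favourable.
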